### Statistical Analysis Plan (SAP)

The confident shoulder study

in clinics and  $\varepsilon_{ijk}$  is the random error assumed to be homogeneous and uncorrelated with mean 0 and variance  $\delta^2$ .

### Model 2

To assess if any potential effect of the intervention on SPADI is also related to time, we shall introduce a time component  $T$  in model 2 and explore how the impact of the intervention develops over time.

$$\text{SPADI}_{ijk} = \beta_0 + \beta_1 I_{ijk} + \beta_2 T_t + \alpha_{ijk} + \varepsilon_{tijk}$$

Here, the parameter estimate  $\beta_2$  represents the effect of time.

### Model 3

Model adjustment of patient level characteristics presented in section 5 above shall be considered in model 3 as follows:

$$\text{SPADI}_{ijk} = \beta_0 + \beta_1 I_{ijk} + \beta_2 T_t + [\beta]X_{ijk} + \alpha_{ijk} + \varepsilon_{tijk},$$

where  $[\beta]$  is a matrix of the patient level covariates. The covariates that we shall consider include the following: patient age, gender, marital status, years of education and occupational status. In addition, GP level covariates such as age, gender, years since graduation, specialty, type of practice, number of GPs in the practice, the number of weekly working hours, and number of people on the GPs' lists at recruitment shall be considered for model adjustment by introducing an additional term,  $[\beta_1]X_{ijk}$  if necessary.

### Model 4

We also believe that the intervention may either decrease SPADI score over time as the GPs gain experience and are confident with the intervention or SPADI scores may increase over time if, for example, the GPs become less enthusiastic about it or if the intervention is not effective. Therefore, we will consider a two-way interaction between time and exposure to the intervention in model 4.

$$\text{SPADI}_{ijk} = \beta_0 + \beta_1 I_{ijk} + \beta_2 T_t + [\beta]X_{ijk} + \beta_3 T_t I_{ijk} + \alpha_{ijk} + \varepsilon_{tijk},$$

The parameter estimate  $\beta_3$  is the interaction between time and exposure to the intervention  $I$  (1 = exposure and 0 = control).

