### 1.2 Study design

A stepped wedge cluster randomized trial (SWCRT) with a focus on assessing the efficacy and feasibility of an evidence-based clinical guideline on shoulder pain management will be taken. The guideline, confident care will be delivered in sequential steps to each GP surgery (cluster) at a pre-determined time point and will be delivered to all the GP surgeries by the end of the study period. This two-year follow-up study will recruit 10 GP surgeries with each GP surgery initially acting as a control (usual care) until it crosses over to receive the confident care.

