#### 3.1 Intention-to-treat (ITT) population

For the intention-to-treat analysis, a binary indicator variable, which denotes whether an observation occurred before or after randomization shall be constructed and used in the regression models. The binary factor shall represent the study months in each general practice pre-randomization and post-randomization. This means that in the ITT population, the general practices shall be analyzed according to their randomized crossover time regardless of whether this was achieved.

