### 4.0 Outcomes

The research data for all patients diagnosed with shoulder pain will be collected from 10 general practices in Østfold County and in the health region of Helse Fonna. The outcomes will be obtained during the entire period of study between January 2020 and 2022 at all pre-specified time points. Therefore, multiple observations per patient are possible.

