#### 4.1 Primary outcome

The primary outcome measure is the Shoulder Pain and Disability Index (SPADI), which is a self-reported questionnaire with 13 items regarding shoulder pain and disability. These are patient level observations obtained at time points 0, 1, 2 and 3 denoting baseline, 6 weeks, 12 weeks and 52 weeks respectively.

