## 6.1 Model building for the primary outcome

To explore the impact of the intervention on SPADI over time, we shall consider building the linear mixed effects regression models in four separate steps. We shall initially ignore the time effect in an unadjusted before and after the intervention model (model 1). Therefore, the SPADI for any given patient  $i$  seen by GP $_j$  in clinic $_k$  (general practice $_k$ ) is given as:

### Model 1

$$\text{SPADI}_{ijk} = \beta_0 + \beta_1 I_{ijk} + \alpha_{ijk} + \varepsilon_{ijk}$$

The parameter estimates  $\beta_0$  and  $\beta_1$  represent the fixed effects associated with the intercept and the effect of the intervention  $I$  (1 = exposed and 0 = unexposed (control)) for patient  $i$  seen by GP $_j$  in clinic  $k$ .  $\alpha_{ijk}$  is the random effect of patients nested by their GPs, who are in turn nested

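### The time term T in Models 2–4 is never defined and no outcome model carries a calendar-period effect, so part of a secular trend can enter the stepped-wedge intervention effect

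*SAP*

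**What the plan says.** Section 1.2 sets out the design. The guideline "will be delivered in sequential steps to each GP surgery (cluster) at a pre-determined time point", and each surgery is a control until it crosses over. "This two-year follow-up study will recruit 10 GP surgeries", and section 4.0 places outcome collection "during the entire period of study between January 2020 and 2022 at all pre-specified time points".

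Section 6.1 builds the SPADI model in four steps:

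- Model 1 has an intercept, the intervention indicator and random effects: "We shall initially ignore the time effect in an unadjusted before and after the intervention model (model 1").
- Model 2: "To assess if any potential effect of the intervention on SPADI is also related to time, we shall introduce a time component", called T. It enters as β2·T_t, one term with one coefficient, explained only as the effect of time.
- Model 3 adds patient covariates and, if needed, GP covariates.
- Model 4 adds T × I, because the intervention may "decrease SPADI score over time as the GPs gain experience and are confident with the intervention", or may fade as enthusiasm wanes.

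Section 6.2 carries the same T into the models for the secondary outcomes. Section 6.1 does not say which of the four models supplies the effect to be reported.

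Two other places bear on time. In section 4.1 the SPADI scores are "obtained at time points 0, 1, 2 and 3 denoting baseline, 6 weeks, 12 weeks and 52 weeks respectively". In section 3.1 study months are used to build the exposure variable: "The binary factor shall represent the study months in each general practice pre-randomization and post-randomization".

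**The concern.** In a stepped wedge, the proportion of exposed practices rises with calendar time, so exposure and calendar time are correlated by design. Any drift in case mix, referral or usual care that shifts SPADI over the study loads partly on the intervention coefficient β1 unless the model has a calendar-period term. The middle periods hold both conditions, which makes the separation possible, but only if the model asks for it.

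No equation in the SAP does so. The months-based factor in section 3.1 is the exposure itself and not an adjustment for period. At stake is whether an estimated difference can be told apart from drift, in the primary analysis and in every secondary one.

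**Working it through.** **1. What could T be?**

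- *Patient follow-up.* Section 4.1 gives the only time codes (0 to 3), and section 6.2 ties the index t to a patient's measurement. This is the most natural reading. Calendar time is then absent from every model.
- *Calendar time.* A single slope removes a linear trend and leaves any other shape. The scores at baseline, 6, 12 and 52 weeks then have no follow-up term.
- *Time since crossover.* This is what the Model 4 rationale describes. It stands in for neither of the other two clocks.

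No reading supplies both calendar period and follow-up.

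**2. The plan's sample size.** Section 2.0 gives 80% power, alpha 0.05, ICC 0.002, a difference of 8 points, 10% dropout and N = 250, but no SD. The SD can be back-solved (two-sided test assumed):

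- n per group = 2 × (1.96 + 0.8416)² × SD² / 8². With SD 21 this is 108.2, so 109 per group and 218 in total.
- Design effect with 22.5 evaluable patients per practice: 1 + 21.5 × 0.002 = 1.043.
- 218 × 1.043 / 0.9 = 252.6, so 253. SD 20 gives 230 and SD 22 gives 276.

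The stated 250 thus corresponds to an SD of about 21 in a parallel-group type of formula without period effects. SD 21 is used below as an assumption.

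**3. Share of a linear trend that enters β1.** Assumptions: 10 practices, equal recruitment per period, 225 evaluable patients (250 × 0.9), one outcome per patient, a random practice intercept, and follow-up balanced over calendar time. The number of steps is not in the SAP, so 2, 5 and 10 are shown. ICC 0.05 is added for comparison.

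A hand check with K steps and periods 0 to K: mean control period = Σj(K−j)/Σ(K−j); mean intervention period = Σj²/Σj.

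- K = 10: 165/55 = 3 and 385/55 = 7, a gap of 4 out of 10 = 0.40.
- K = 5: 20/15 = 1.333 and 55/15 = 3.667, a gap of 2.333 out of 5 = 0.47.
- K = 2: 1/3 and 5/3, a gap of 1.333 out of 2 = 0.67.

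The generalised least squares results agree. Power is Φ(8/SE − 1.96).

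| Steps | ICC | Share of trend in β1, no period term | SE without → with period effects | Power for 8 points |
|---|---|---|---|---|
| 2 | 0.002 | 0.670 | 2.80 → 4.88 | 0.81 → 0.37 |
| 2 | 0.05 | 0.709 | 2.82 → 5.22 | 0.81 → 0.33 |
| 5 | 0.002 | 0.471 | 2.81 → 3.87 | 0.81 → 0.54 |
| 5 | 0.05 | 0.531 | 2.91 → 4.25 | 0.78 → 0.47 |
| 10 | 0.002 | 0.405 | 2.81 → 3.65 | 0.81 → 0.59 |
| 10 | 0.05 | 0.469 | 2.96 → 4.06 | 0.77 → 0.50 |

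With categorical period effects the share is zero in every row.

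**4. In SPADI points.** The drift is an assumption. For 10 single-practice steps (11 periods), intervention data lie 4 × 12/11 = 4.36 months later than control data if recruitment lasts 12 months, and 4 × 24/11 = 8.73 months later if it lasts 24.

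| Drift per month | Bias, 12-month recruitment | Bias, 24-month recruitment |
|---|---|---|
| 0.25 | 1.1 | 2.2 |
| 0.5 | 2.2 | 4.4 |

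Across the layouts in step 3, a total drift of 4 points over the study gives a bias of 1.6–2.8 points and a two-sided type I error of about 9–17%. A total drift of 8 points gives 3.2–5.7 points and about 21–52%.

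**The case against.** The strongest reply is that T may be meant as calendar time, in which case a linear trend is already handled. Section 6.1 does not rule this out, and a reader who infers that the SAP defines T as patient follow-up goes further than the text, which leaves T undefined. The reply does not rescue the plan: a non-linear trend would remain and the repeated scores would lose their follow-up term. Nor is a straight line certain to be intended, since the notation is loose and section 23's subject, incidence rate ratios, is discussed in section 6.0 by time point. The single coefficient is simply what the equations show.

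Three further limits stand. A reader might infer that the whole of a secular trend is counted as effect; the calculation puts it at about 40–70% of a linear trend. A reader might also take follow-up time to be balanced between conditions. Section 3.1 attaches exposure to the date of the observation, so late visits would be exposed more often. With even recruitment over 12 months and even crossover over 24 (both assumed), about 6/24 = 25% of baseline scores but 18/24 = 75% of 52-week scores would be exposed. The shares in the table rest on balance and would change under that rule; the need for both terms becomes greater. Finally, two years that include 52-week outcomes point to recruitment of about 12 months, so the smaller biases deserve at least equal weight.

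Model 1 is openly labelled unadjusted and a first step, which is fair. But no model is named as the one for inference. A linear calendar term is a possible alternative to categorical periods, but in the layouts examined its SE was the same to two decimals, so it saves no precision there.

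**Conclusion.** The point holds. T is undefined, no primary or secondary outcome model specifies a calendar-period effect, and no single reading of T covers both calendar time and follow-up. Under the follow-up reading the equations as written leave a substantial part of any secular trend in β1.

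The structural fault needs no assumed figure; its size does. The drift, the number of steps, the recruitment span and the SD are not in the SAP, and nothing in it shows that a drift will occur. It would be wrong to infer that the estimate is biased by a known amount. What can be said is that moderate drifts would produce biases that are material against a target difference of 8 points. This should be corrected before analysis.

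**What to change.** - Define T in section 6.1, and use separate symbols for calendar period, follow-up visit and time since crossover.
- Add fixed calendar-period (step) effects, preferably categorical, to every primary and secondary model from which an intervention effect is concluded.
- Keep follow-up visit as a separate categorical factor, with the 12-week contrast as primary, in line with the objective in section 1.3.
- State that Model 1 is descriptive only.
- If the GP-experience question is kept, model it as time since the practice's crossover in a secondary analysis rather than as T × I.
- Recheck and restate the 80% power under the period-adjusted model.

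The cost is SAP wording and a real loss of precision. Under SD 21 and the layouts above, the SE rises from about 2.8–3.0 to 3.7–5.2 points and power for 8 points falls from about 0.8 to 0.33–0.59. These figures allow no gain from baseline SPADI or from repeated measures, which may recover part of the loss.

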## 6.2 Model building of secondary outcomes

We shall also consider similarly structured models for secondary outcomes if the measurement scale is either continuous or categorical. In a binary logistic regression setting with patient, GP and clinic random effects and adjusted for patient level covariates and time, the binary responses  $Y_{tijk}$  shall be modelled by considering a model of the form:

$$Y_{tijk} \sim \text{Binomial}(1, p_{tijk})$$

$$\text{logit}(p_{tijk}) = \beta_0 + \beta_1 I_{ijk} + \beta_2 T_t + [\beta] X_{ijk} + \beta_3 T_t I_{ijk} + \alpha_{ijk} + \varepsilon_{tijk}$$

$Y_{tijk}$  is 1 if patient  $i$  at time  $t$  seen by GP  $j$  in clinic  $k$  had for example, sick leave and 0 otherwise.

The parameter estimates are defined as in model 4 above.

However, for count data such as the number of sick leave, a model of the form below shall be considered;

$$\log[E(Y|x_{ijk})] = \beta_0 + \beta_1 I_{ijk} + \beta_2 T_t + [\beta] X_{ijk} + \beta_3 T_t I_{ijk} + \alpha_{ijk}$$

where  $E(Y|x_{ijk})$  is the expectation of  $Y$ , which is a vector of count response variables given the covariates  $X_{ijk}$  and the parameter estimates  $\beta_0$ ,  $\beta_1$ ,  $\beta_2$ ,  $[\beta]$  and  $\beta_3$  are as described above.

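### Model 4 is justified by GPs gaining experience or losing enthusiasm, but no model contains time since crossover and T is undefined, so its interaction cannot be read as either

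*SAP*

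**What the plan says.** SAP section 6.1 introduces Model 4 with two opposing expectations. One is that "the intervention may either decrease SPADI score over time as the GPs gain experience and are confident with the intervention"; the other is that "SPADI scores may increase over time if, for example, the GPs become less enthusiastic about it or if the intervention is not effective". It then concludes: "Therefore, we will consider a two-way interaction between time and exposure to the intervention in model 4". The added term is β3·T_t·I_ijk.

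T enters at Model 2, where the SAP says only that "we shall introduce a time component" T. Its scale is not given. The only time points that the SAP numbers are in section 4.1, where SPADI values are "patient level observations obtained at time points 0, 1, 2 and 3 denoting baseline, 6 weeks, 12 weeks and 52 weeks respectively". Section 6.2 indexes the response by patient and time t, and carries the same T_t·I_ijk term into the binary and count models.

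The exposure variable I is binary. Section 3.1 builds it from study months before and after randomisation in each practice. The per-protocol factor in section 3.2 has three levels. Neither records how long a practice has been using the guideline.

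**The concern.** Experience and loss of enthusiasm belong to the practice and grow with time since its crossover. To test them, a model must tell a patient included just after crossover from one included many months later. None of Models 1 to 4 does so.

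Section 6.1 attaches a mechanism to each direction of change. A reader of the results would therefore tend to take a negative β3 as GPs improving and a positive one as waning. If T is the patient's visit, β3 instead reflects the course of an individual patient, and a lasting benefit is enough to make it negative. The trial could then report a learning effect where there was none, or where the effect was fading. That would mislead anyone asking whether the guideline's benefit is sustained in practice.

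**Working it through.** **Plan's own figures.** The SAP gives no figure for β3. The nearest is 250 patients for 8 points (section 2.0: 80% power, alpha 0.05, ICC 0.002, 10% dropout), with no SD stated. A simple two-group formula gives a plausible SD: n per group = 2(1.960 + 0.842)²·SD²/8², design effect 1 + (25 − 1)×0.002 = 1.048 (25 = 250/10 practices), then division by 0.9.
- SD 20: 98.1 → 99 per group; 198 × 1.048 = 207.5 → 208; 208/0.9 = 231.1 → 232.
- SD 21: 255.

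So 250 corresponds to an SD of about 21. This neither confirms nor refutes the plan's figure, but it makes SD 20 a reasonable central assumption.

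**β3 when T is the visit.** Assume complete data, a patient random intercept and I fixed per patient. Let e_t be the exposed-minus-control difference at visit t. Then β3 = Σ(t − t̄)e_t / Σ(t − t̄)².

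For T = 0, 1, 2, 3 the deviations are −1.5, −0.5, 0.5, 1.5, with sum of squares 5. For T in weeks (0, 6, 12, 52; mean 17.5) they are −17.5, −11.5, −5.5, 34.5, with sum of squares 1659.

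| Difference at baseline, 6, 12, 52 weeks | β3 per visit | β3 per week |
|---|---|---|
| 0, −8, −8, −8 | −12/5 = −2.4 | −140/1659 = −0.084 |
| 0, −8, −8, −4 | −6/5 = −1.2 | −2/1659 = −0.001 |
| 0, −8, −8, 0 | 0 | +136/1659 = +0.082 |

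No row involves GP learning. β3 follows the patient's course.

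**Chance of significance for 0, −8, −8, −8.** SE = √[SD²(1 − ρ)/Σ(t − t̄)² × 2/112.5], with 250 × 0.9 = 225 patients split equally (assumed).
- Visits, SD 20, ρ 0.5: SE = √(200/5 × 2/112.5) = 0.84; z = 2.4/0.84 = 2.85; power about 81%. Over SD 15–25 and ρ 0.3–0.7: 49% to over 99%.
- Weeks, same centre: about 45%; range 23–88%.

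**Simulation, T = 0–3, SD 20, ρ 0.5, ICC 0.002, 10 practices, 1000 trials per scenario.** Set A: 250 patients, 12 months' recruitment, one practice crossing per step. Set B: 225 patients, 24 months' recruitment, five sequences (ten gave similar results).

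| True effect across the rollout | A: significant | B: mean β3; negative; significant |
|---|---|---|
| None | 6% | 0.03; 49%; 6% |
| Constant 8 | 86% | −2.45; 99.7%; 83% |
| Waning (A 12 to 4; B 12 to 0) | 93%, all with negative sign | −2.25; 99.7%; 77% |
| Learning (4 to 12) | 72% | −2.07; 99%; 70% |

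β3 is no more negative under learning than under waning, so its sign cannot separate them.

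**Other readings.**
- I varying by observation, T = visit: constant effect gives mean −1.83, significant in 41%; under waning, β3 is still negative in 96%.
- T = calendar month of enrolment: a constant effect is significant in about 5–7%, so size is about right. Mean β3 has the expected sign under waning (+0.26) and learning (−0.14). Power for learning is 6% for a 4-to-12 change (set B) and 11% for 0-to-16 (set A).

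**A time-since-crossover term.** With a constant effect it is significant in about 5% in both sets. In set B its sign is wrong in only 3% of trials under 12-to-0 waning and is right in 88% under 4-to-12 learning. Power for a 4-to-12 change is 38% in A and 19% in B; for 0-to-16 it is 91% in A.

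**The case against.** The strongest reply is that T is undefined rather than wrongly defined. Section 4.1 numbers the SPADI assessments but does not link them to T, a patient observed at time t could equally be placed in calendar time, and the GP-experience rationale itself suggests study time. This stands: follow-up time is an inference, although the best supported one. It does not rescue Model 4, because with T as enrolment month the term can hardly detect the hypothesis written for it.

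A reader might infer that β3 will be significant and negative whenever the intervention works. The documents do not support that. Significance depends on SD, correlation, the coding of T and whether I varies by observation. A benefit gone by 52 weeks gives a β3 of zero (visits) or above zero (weeks).

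Nor does the SAP lay down a rule that a negative β3 means learning. It calls β3 simply the time-by-exposure interaction, and it also names an ineffective intervention as a reason for rising scores, which is not a matter of GP experience. Still, the rationale invites that interpretation.

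Finally, Model 4 is one model-building step, while the primary objective in section 1.3 is the 12-week comparison. That limits the consequence. The baseline mechanism also does not reach global improvement and satisfaction, which section 4.2 says have no baseline measurement; the absence of time since crossover does.

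**Conclusion.** The point holds in a limited form. The hypothesis stated for Model 4 concerns time since crossover, no model contains that time, and T needs a definition. On neither reading should β3 be interpreted as GP experience or waning: on the visit reading it answers a different question, and on the enrolment-month reading it has almost no power for the stated one.

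The figure of −2.4 per visit follows by arithmetic from a constant 8-point benefit, an equal baseline and persistence to 52 weeks. The probabilities rest on assumptions absent from the SAP: SD 15–25, within-patient correlation 0.3–0.7, the number of steps, uniform recruitment and complete data.

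The damage is to the interpretation of β3, not to the stated 12-week objective. It is worth correcting before analysis, but it does not threaten the trial.

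**What to change.** - State what T is in Models 2 to 4.
- For the experience or waning question, add to Model 4 a term for months from the practice's randomised crossover to the patient's inclusion, applied to exposed patients at post-baseline visits (zero otherwise).
- Keep visit as a factor with exposure-by-visit terms, reported as the patient's course, and keep calendar time as a separate term so that secular change is not taken for experience.
- Interpret only the time-since-crossover coefficient as experience or waning, and label it exploratory.
- Use the same term in section 6.2, dropping the post-baseline factor for global improvement and satisfaction.

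The cost is revised wording and one variable derived from crossover and inclusion dates that the trial must already hold; no new data are needed. The drawbacks are one more term and modest power, about 19–38% for a 4-to-12-point change under the assumed recruitment and steps, so a non-significant result would not show that the effect is stable.

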## 6.2 Model building of secondary outcomes

We shall also consider similarly structured models for secondary outcomes if the measurement scale is either continuous or categorical. In a binary logistic regression setting with patient, GP and clinic random effects and adjusted for patient level covariates and time, the binary responses  $Y_{tijk}$  shall be modelled by considering a model of the form:

$$Y_{tijk} \sim \text{Binomial}(1, p_{tijk})$$

$$\text{logit}(p_{tijk}) = \beta_0 + \beta_1 I_{ijk} + \beta_2 T_t + [\beta] X_{ijk} + \beta_3 T_t I_{ijk} + \alpha_{ijk} + \varepsilon_{tijk}$$

$Y_{tijk}$  is 1 if patient  $i$  at time  $t$  seen by GP  $j$  in clinic  $k$  had for example, sick leave and 0 otherwise.

The parameter estimates are defined as in model 4 above.

However, for count data such as the number of sick leave, a model of the form below shall be considered;

$$\log[E(Y|x_{ijk})] = \beta_0 + \beta_1 I_{ijk} + \beta_2 T_t + [\beta] X_{ijk} + \beta_3 T_t I_{ijk} + \alpha_{ijk}$$

where  $E(Y|x_{ijk})$  is the expectation of  $Y$ , which is a vector of count response variables given the covariates  $X_{ijk}$  and the parameter estimates  $\beta_0$ ,  $\beta_1$ ,  $\beta_2$ ,  $[\beta]$  and  $\beta_3$  are as described above.

